10.2.4.2 Study Medication Discontinuation

Study medication should be permanently discontinued in the event of any of the following:

- Severe infection requiring parenteral antimicrobial therapy or hospitalization
- Symptomatic herpes zoster
- Malignancy – except for non-melanoma skin cancer (e.g. squamous or basal cell carcinoma) not in or near the treatment area
- Anaphylactic or severe allergic reaction
- WBC Count: $< 1 \times 10^9/L$ or second occurrence of $< 2 \times 10^9/L$
- ANC: $< 0.5 \times 10^9/L$ or second occurrence of $< 1 \times 10^9/L$
- Lymphocyte count: $< 0.3 \times 10^9/L$ or second occurrence of $< 0.5 \times 10^9/L$
- Platelet count: $< 50 \times 10^9/L$ or second event of $< 75 \times 10^9/L$ - in each case, value should be confirmed by retesting before treatment discontinuation
- Hemoglobin: $< 6.5 \text{ g/dL}$ or second occurrence of $< 8 \text{ g/dL}$ - in each case, value should be confirmed by retesting before treatment discontinuation
- AST or ALT:
 - $> 5 \times \text{ULN}$ persisting for 1 week of study medication interruption or second event of $> 5 \times \text{ULN}$
 - $> 3 \times \text{ULN}$ with total bilirubin $> 2 \times \text{ULN}$ or symptoms of hepatocellular injury (fatigue, nausea, vomiting, right upper quadrant pain or tenderness, fever, rash and/ or eosinophilia ($> 5\%$)).
- Serum creatinine: $> 2 \times \text{ULN}$ persisting for > 2 weeks of treatment discontinuation or second occurrence of $> 2 \times \text{ULN}$

The continued treatment of subjects who experience other serious or severe adverse events considered related to study treatment should be discussed with the Sponsor's medical monitor.

11. PREGNANCY

11.1. Definition of Women of Child Bearing Potential (WOCBP)

WOCBP includes any female who has experienced menarche and who has not undergone successful surgical sterilization (e.g., hysterectomy, bilateral tubal ligation, or bilateral oophorectomy) or is not postmenopausal. Postmenopausal is defined as ≥ 12 months with no menses without an alternative medical cause. WOCBP must have a negative serum pregnancy test at Screening (Visit 1) and a negative UPT at Baseline (Visit 2) prior to randomization.

11.2. Highly Effective Methods of Birth Control

The Investigator or subinvestigator will discuss the potential risk factors associated with pregnancy and the importance of maintaining a highly effective method of contraception throughout the study with all WOCBP (for example, those which result in a low failure rate - i.e., less than 1% per year when used consistently and correctly). All WOCBP must use a highly effective method of birth control during the study and for 30 days after the final application of study medication in a manner such that risk of failure is minimized.

Highly effective methods include:

- Combined (estrogen and progestogen containing) hormonal contraception associated with inhibition of ovulation

- oral
 - intravaginal
 - transdermal
- Progestogen-only hormonal contraception associated with inhibition of ovulation:
 - oral
 - injectable
 - implantable
- intrauterine device (IUD)
- Obstruction of fallopian tubes via medical device (Essure™)
- intrauterine hormone-releasing system (IUS)
- vasectomized partner¹
- sexual abstinence²

¹Vasectomized partner is a highly effective birth control method provided that partner is the sole sexual partner of the WOCBP trial participant and that the vasectomized partner has received medical assessment of the surgical success.

² Sexual abstinence is considered a highly effective method only if defined as refraining from heterosexual intercourse during the entire period of risk associated with the study treatments (study duration and 30 days after the last study medication application). The reliability of sexual abstinence needs to be evaluated in relation to the duration of the clinical trial and the preferred and usual lifestyle of the subject.

WOCBP must be on a highly effective method of birth control for the following timeframes prior to study entry:

- Implants (on a stable dose for ≥90 days)
- Injectables (on a stable dose for ≥90 days)
- Patches (on a stable dose for ≥90 days)
- Combined oral contraceptives (on a stable dose for ≥90 days)
- Intrauterine devices (inserted for ≥30 days)

Prior to trial enrollment, WOCBP must be advised of the importance of avoiding pregnancy during trial participation and of the potential risk factors associated with pregnancy while in study. The subject must sign an informed consent form documenting this discussion. During the trial, all WOCBP will be instructed to contact the investigator immediately if they suspect they might be pregnant (e.g., missed or late menstrual period).

If a subject or investigator suspects that the subject may be pregnant prior to study medication administration, the study medication must be withheld until the results of a pregnancy test are available. If pregnancy is confirmed, the subject must not receive study medication and must be discharged from the study.

If, following study medication administration, it is determined that the subject may have been or was pregnant at the time of study medication exposure (including at least 2 days after study medication administration) the investigator must immediately notify the Aclaris Therapeutics, Inc. Medical Monitor and record the event on a pregnancy surveillance form. While not an AE or SAE, the investigator must report every pregnancy using a pregnancy surveillance form and follow the reporting procedures described for SAE reporting.

Protocol-required procedures for trial discontinuation and follow-up must be performed on the subject unless contraindicated by pregnancy (e.g., x-ray studies). Other appropriate pregnancy

follow-up procedures should be considered if indicated. In addition, the investigator must report to Aclaris Therapeutics, Inc.'s Medical Monitor on the pregnancy surveillance form, follow-up information regarding the course of the pregnancy, including perinatal and neonatal outcome. Infants should be followed for a minimum of six weeks.

12. STATISTICAL ANALYSES

12.1. Sample Size and Power Calculations

The planned sample size is 12 subjects. This is the first multicenter study evaluating the effect of ATI-50002 Topical Solution in subjects with stable alopecia universalis and alopecia totalis. No formal power calculations will be performed.

12.2. Analysis Populations

Pharmacokinetic and Pharmacodynamic study populations will be described in a Statistical Analysis Plan and finalized prior to database lock.

12.3. Demographic and Baseline Characteristics

Subject demographic and baseline characteristics, including medical and alopecia history, prior medications and therapies and physical examination findings will be summarized using descriptive statistics.

For continuous variables, descriptive statistics (number, mean, standard deviation, standard error, median, minimum, and maximum) will be provided. For categorical variables, subject counts and percentages will be provided. Categories for missing data will be presented, if necessary.

12.4. Pharmacokinetic Analyses

Blood Samples

Blood samples for analysis of the concentration of ATI-50002 will be taken from the first 6 subjects enrolled into the study on Baseline/Day 1 (Visit 2) and Day 29 (Visit 7) at predose (0 hr), and 1, 2, 4, 8 hours after study medication application and on Day 2 (Visit 3) and Day 29 (Visit 7), 24 hours post dose. For each subject, standard PK parameters (C_{max} , T_{max} , AUC_{0-t} , $AUC_{0-\infty}$, $t_{1/2}$) will be calculated, as a minimum and whenever possible, based on the plasma concentrations of ATI-50002.

Scalp Biopsy

The concentration of ATI-50002 in skin will be determined in a 4-mm punch biopsy of the scalp taken on Day 2 (Visit 3) and Day 29 (Visit 7) 24 hours post study medication application in the office on Day 1(Visit 2) and Day 28 (Visit 6).

12.5. Pharmacodynamic (Biomarker) Analyses

12.5.1. ALADIN Scores

The cytotoxic T-lymphocyte infiltration (CTL), Interferon (IFN-gamma), and hair keratin (KRT) ALADIN scores will be calculated for each scalp biopsy sample as previously described in (Xing

et al, 2014, Jabbari 2016). Change in ALADIN scores within individual subjects will be assessed between Baseline/ Day 1 (Visit 2), Day 29 (Visit 7) and Week 28 (Visit 13) for subjects enrolled in the open-label extension.

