1. SYNOPSIS

Protocol Number: ATI-50002-AA-202	Protocol Title: Double-blind, Vehicle-controlled Multicenter Study to Evaluate the Safety, Tolerability, Pharmacokinetics and Pharmacodynamics of ATI-50002 Topical Solution Administered Twice-Daily for 28 Days in Adult Subjects with Alopecia Universalis and Alopecia Totalis with a 12-Month, Long-Term, Open-Label Extension
Sponsor: Aclaris Therapeutics Inc.	Phase of Development: Phase 2
Study Medication Description: ATI-50002 Topical Solution, 0.46% Vehicle Topical Solution	
Study Objectives: Primary: To assess safety, tolerability, pharmacokinetics and pharmacodynamics of ATI-50002 Topical Solution, 0.46% compared to vehicle in subjects with alopecia universalis (AU) and alopecia totalis (AT) Secondary Objectives: To assess the efficacy of ATI-50002 Topical Solution, 0.46% for the treatment of scalp hair loss and eyebrow in subjects with AU or AT. To assess subject satisfaction following treatment with ATI-50002 Topical Solution, 0.46% for the treatment of scalp hair loss in subjects with AU or AT.	

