4. STUDY RATIONALE

4.1. Study Rationale

Preclinical and preliminary clinical information, as discussed above, strongly suggests that the primary pathophysiologic mechanism in AA (including AT and AU) is a cytokine-mediated (primarily through T-lymphocyte induced upregulation of IL-15 and IFN gamma) induction of and prolonged maintenance of the telogen stage of the hair cycle. Inhibitors of the JAK/STAT pathway, particularly JAK1 and JAK3, are known to downregulate the effects of both IFN-gamma (through the inhibition at JAK1), and IL-15 (through inhibition at both JAK1 and JAK 3), and several published case reports have demonstrated the potential for compounds that are JAK1/3 inhibitors to induce hair growth in patients with AA, AU and AT. As ATI-50002 is a potent inhibitor at JAK 1 and JAK 3, it is strongly suggested that ATI-50002 may be effective in the treatment of AA, AU and AT.

The double-blind period of the study will evaluate the safety, tolerability, pharmacokinetics and pharmacodynamics of ATI-50002 Topical Solution, 0.46% compared to Vehicle Topical Solution applied twice-daily for 28 days in subjects with AU or AT. On Day 1 (Visit 2) and Day 28 (Visit 6), study medication will only be applied once a day. The study will include the assessment of the scalp hair loss at Baseline (Visit 2) and Day 29 (Visit 7) by both SALT and ALODEX. Early signs of hair regrowth are expected to take a minimum of 3 to 6 months in this population. Measurable hair regrowth may take at least 6 months or longer. Data from SALT and ALODEX will be described but no formal statistical comparisons will be made between Day 1 (Visit 2) and Day 29 (Visit 7) assessments.

Subjects who complete the double-blind period without any clinically significant adverse events or tolerability issues as assessed by the Investigator and who continue to meet the entry criteria will have the option to enroll in the open-label extension. The open-label period will evaluate the safety, tolerability and efficacy of ATI-50002 Topical Solution, 0.46% for the treatment of subjects with AU or AT. Subjects will apply ATI-50002 Topical Solution 0.46% to the entire

scalp, twice daily for 12 months. In addition, subjects with eyebrow loss may apply a thin film of study medication to the affected eyebrow(s) twice-daily for 12 months.

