5. STUDY OBJECTIVE

5.1.1. Primary Objective

The primary objective is to assess the safety, tolerability, pharmacokinetics and pharmacodynamics of ATI-50002 Topical Solution, 0.46% in subjects with AU or AT.

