### 1. STUDY OBJECTIVES

#### 1.1 Primary Objective

To assess safety, tolerability, pharmacokinetics and pharmacodynamics of ATI-50002 Topical Solution, 0.46% compared to vehicle in subjects with alopecia universalis (AU) and alopecia totalis (AT).

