### **4.3.1 ALADIN Scores**

The analysis of ALADIN scores will be detailed in a separate document.

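### Neither the protocol nor the SAP states an active-versus-vehicle contrast for ALADIN, although the pharmacodynamic objective is framed against vehicle

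*Protocol*

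**What the plan says.** The objective is stated in two ways. SAP 1.1 reads: "To assess safety, tolerability, pharmacokinetics and pharmacodynamics of ATI-50002 Topical Solution, 0.46% compared to vehicle in subjects with alopecia universalis (AU) and alopecia totalis (AT". The protocol synopsis agrees ("pharmacokinetics and pharmacodynamics of ATI-50002 Topical Solution, 0.46% compared to vehicle"), and so does the study rationale in 4.1, which describes the double-blind period as evaluating "pharmacodynamics of ATI-50002 Topical Solution, 0.46% compared to Vehicle Topical Solution applied twice-daily for 28 days". Protocol 5.1.1 leaves the comparator out: "The primary objective is to assess the safety, tolerability, pharmacokinetics and pharmacodynamics of ATI-50002 Topical Solution, 0.46% in subjects with AU or AT".

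Three ALADIN scores are to be derived from each biopsy: "The cytotoxic T-lymphocyte infiltration (CTL), Interferon (IFN-gamma), and hair keratin (KRT) ALADIN scores will be calculated" (protocol 12.5.1). The only analysis described for them, there and in the synopsis, is: "Change in ALADIN scores within individual subjects will be assessed between Baseline/ Day 1 (Visit 2), Day 29 (Visit 7) and Week 28 (Visit 13", with the last visit applying to subjects in the open-label extension. The SAP adds no method: "The analysis of ALADIN scores will be detailed in a separate document". SAP 4.8 repeats the deferral and extends it to the blood T-cell work.

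Two other SAP statements bear on the point. Section 4 sets a general rule that summaries are laid out by double-blind arm. Section 4.8 says that the biopsy histology will not be analysed.

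**The concern.** A vehicle-controlled objective needs a quantity that compares the arms. Change from baseline in a subject on ATI-50002 mixes any drug effect with whatever else moves the score between two biopsies. That could include an effect of the solution base, which contains DMSO and propylene glycol (protocol 8.1), an effect of earlier biopsies, a difference in assay runs between visits, or ordinary fluctuation. The documents do not show that any of these occurs. The randomised vehicle arm is there so that nobody has to assume they are absent.

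If the pharmacodynamic result is read from within-subject change on drug, a shift shared by both arms can pass as drug activity. The primary objective would then be answered without the control it names.

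**Working it through.** **Does any other planned analysis supply the vehicle comparison?**

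- Histology: dropped (SAP 4.8).
- Blood T-cells: deferred with ALADIN (SAP 4.8).
- SALT and ALODEX: tabulated by visit and arm under the SAP's pharmacodynamic heading, but protocol section 9 does not expect regrowth within the 28 double-blind days.
- Week 28 ALADIN: taken only from extension subjects, all of whom apply ATI-50002 (protocol 7.1), so it has no concurrent vehicle arm.
- Day 29 ALADIN: biopsies are scheduled in both randomised arms at Baseline and Day 29 (protocol 7.1 and 7.3). This is the one controlled reading, and neither document states a contrast for it.

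**The plan's own figure.** The sample size is 12 at 2:1: 12 × 2/3 = 8 active and 12 × 1/3 = 4 vehicle, as the synopsis states. It was set by feasibility (SAP 4.7). There is no alpha, SD or effect size to reproduce.

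**Precision of the missing contrast.** Assume normal changes with a common SD, and express results in units of that SD. The 95% half-width for a difference in mean change is t(0.975, n1+n2−2) × √(1/n1 + 1/n2).

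- 8 v 4 pairs: 2.228 × √(1/8 + 1/4) = 2.228 × 0.612 = 1.36 SD.
- 8 v 2 pairs: 2.306 × √(1/8 + 1/2) = 2.306 × 0.791 = 1.82 SD.
- For comparison, the within-active mean alone with 8 pairs: 2.365 / √8 = 0.84 SD.

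The narrower within-arm interval describes a different quantity, namely drug effect plus any common shift.

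**How a common shift would look (illustration).** Assume a two-sided 0.05 level, which the documents do not state, no drug effect, and the same mean shift of d SD in both arms. A one-sample t reading of the 8 active subjects has noncentrality d√8 on 7 degrees of freedom. The active-minus-vehicle comparison has noncentrality 0 whatever d is.

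| Common shift d | d√8 | Active arm alone looks positive | Active minus vehicle looks positive |
|---|---|---|---|
| 0 | 0 | 5% | 5% |
| 0.25 SD | 0.71 | 9% | 5% |
| 0.5 SD | 1.41 | 23% | 5% |
| 1.0 SD | 2.83 | 68% | 5% |

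The values of d are assumptions with no source in the documents.

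**The case against.** The best reply is that 12.5.1 merely defines a variable. Each subject's change from baseline is also the input to an active-minus-vehicle difference. Nothing there says that arms will be pooled, that vehicle will be ignored or that within-arm tests will be run. SAP section 4 lays summaries out by arm by default, and a side-by-side display would normally expose a shift common to both. The contrast may also stand in the separate ALADIN document. All of this is fair, and it limits the point to what the protocol and SAP state. What remains is that a general display rule is not a contrast: it gives neither the difference nor its uncertainty.

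Several stronger readings are tempting, and the documents do not support them.

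- A reader might infer that no vehicle comparison of ALADIN was ever planned. The separate document is unseen, so this cannot be said.
- A reader might take the percentages above as the plan's false-positive rate. No test or alpha is planned for ALADIN, and the one between-arm test in the protocol, the chi-square on adverse events, was dropped (SAP 4.8).
- A reader might suppose that 8 against 4 by itself produces the pattern of change on drug and none on vehicle. Without a shift, that pattern has probability 0.05 × 0.95 = 4.75%. It becomes common only if a shift is assumed.
- A reader might count three scores at two times as six equivalent chances of a positive result. Week 28 is a different group: extension subjects only, possibly including former vehicle subjects. It is not the 8 randomised active subjects.
- A reader might infer from SAP 4.6 that ALADIN results had been seen before a method was fixed. That section reports an interim look at blood and scalp PK in the first six subjects and speaks of unblinded PK/PD review. It does not say that ALADIN scores were opened, and the ALADIN document carries no stated date. The order of events is unknown.

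Insisting on one lead score would also be a debatable preference in an unpowered 12-subject study with no success rule.

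**Conclusion.** The point holds in limited form. The vehicle-framed pharmacodynamic objective has no matching ALADIN contrast in the protocol or SAP, and 5.1.1 states the objective differently from the synopsis, rationale and SAP 1.1. The by-arm display lowers the risk of misreading but does not remove it. Only the Baseline-to-Day 29 change can answer the question with a randomised control.

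The answer will be imprecise: about ±1.36 SD if all 8 and 4 pairs are evaluable. The number of evaluable pairs is not known. Histology and RNA sequencing are both assigned to the PD biopsy (protocol 9.2.1), and histology was abandoned for limited samples, so fewer ALADIN pairs are possible. These figures rest on normal changes and equal SDs in the two arms. The common-shift percentages also rest on an assumed 0.05 level and assumed shifts, and only illustrate why the control should be used.

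**What to change.** In protocol 12.5.1 and the ALADIN analysis document:

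- Report the ATI-50002 minus vehicle difference in Baseline-to-Day 29 change, with a 95% confidence interval and the number of evaluable pairs per arm, for each of the three scores.
- Give the three differences equal rank as descriptive estimates, unless a lead score was named before unblinded data were seen. State the date of the ALADIN document relative to unblinding.
- Label within-subject changes, and everything at Week 28, as uncontrolled.
- Align 5.1.1 with the vehicle comparison in the synopsis, rationale and SAP 1.1.

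The cost is wording and one extra table. No new samples are needed, because both arms are already scheduled for biopsy at Baseline and Day 29. The drawback is the wide interval. If the contrast were tested at two-sided 0.05 with 8 v 4 pairs, power would be about 32% for a true difference of 1 SD and 84% for 2 SD. This is why an estimate with its interval suits the study better than a test.

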12.5.2. Histology

Scalp punch-biopsies will be formalin-fixed and paraffin-embedded and will be sectioned both vertically and horizontally by a qualified dermatopathologist. Specimens will be stained with hematoxylin and eosin (H&E) for “routine” histopathologic evaluation that will include (but is not limited to) diagnosis and evaluation of the presence, quantity, location, and quality of any hair, hair follicles, and inflammatory infiltrate present. Additionally, immunohistochemical (IHC) stains will be employed to identify immune cell populations (e.g., Lymphocytes, cytotoxic T-lymphocytes (CTLs)), and hair-specific keratins. IHC stains to assess inflammatory responses will include but not be limited to, CD8, HLA-DR and ICAM-1. Data will be presented as percent change from baseline in the number of cells/ high power field in regions of interest (peribulbar areas) and in percent change from baseline in the number of cells/mm².

12.5.3. Blood for Immunology

Blood samples will be stained with cell surface antibodies for fluorescence acquisition cell sorting (FAC) analysis. FACS experiments will allow for assessment of the subset and activation status of immune cells involved in AA.

12.5.4. Secondary Analyses

Summary descriptive statistics (N, mean, median, SD) by visit will be provided for all efficacy parameters. Secondary efficacy parameters are described below:

The secondary efficacy endpoints include mean change from baseline in the SALT score at Week 28 (Visit 13), Week 40 (Visit 14) and Week 52 (Visit 15).

The percentage hair growth will be calculated as the mean change from Baseline (Visit 2) scores compared to end of treatment Week 28 (Visit 13), Week 40 (Visit 14) and Week 52 (Visit 15).

Mean change from baseline in the ALODEX score, proportion of subjects achieving a $\geq 50\%$ hair growth compared with baseline.

Treatment satisfaction will be summarized.

The ALODEX score analysis will use the same methodology as specified for SALT score analysis. Other parameters will be analyzed as detailed in the statistical analysis plan.

Mean change from baseline in eyebrow growth will be calculated as the mean change in the Clinician’s Eyebrow Assessment (CEA) from entry into the long-term, open-label extension compared to Week 28(Visit 13), Week 40 (Visit 14) and Week 52 (Visit 15). The CEA evaluates eyebrows on a scale from “No eyebrow hair” (Grade 0) to “Full eyebrow hair” (Grade 4).

Mean change from baseline in the Subject's Eyebrow Assessment (SEA) will be calculated from entry into the long-term open label extension to Week 28 (Visit 13), Week 40 (Visit 14) and Week 52 (Visit 15). The SEA evaluates eyebrows on a scale from "No eyebrow hair" (Grade 0) to "Full eyebrow hair" (Grade 4).

12.6. Safety Analyses

Safety analyses will include descriptive statistics calculated on the safety parameters using the safety population. The proportion of subjects with treatment-emergent adverse events will be tabulated and presented by treatment and Medical Dictionary for Regulatory Activities (MedDRA) System Organ Class. Vital signs and clinically significant abnormal laboratory results will also be tabulated and presented by treatment group. Overall incidence of adverse events will be compared between groups using a chi-square test.

Data from all randomized subjects will be presented and summarized. Safety summaries by study treatment group will include listings by study medication of adverse events incidences within each MedDRA System Organ Class, and changes from pre-application values in vital signs.

Adverse event summaries will be presented by study medication showing the proportion of subjects experiencing adverse events, both overall and by MedDRA System Organ Class.

